### 1.3.2. Part 1 & Part 2 Challenge Visits

Visit (V)	V1, V2 (Part 2 only)					Follow-up phone call (5-7 days post last challenge day)	Early withdrawal	Notes
Procedure	Pre-challenge	Within 1 h before first control challenge	At least 20 min before first SP challenge	SP challenges	2 h after last SP challenge			
Clinical chemistry/Haematology and urinalysis		X			X*		X	*In Part 2, 2 h post last SP challenge at last challenge visit only.
12-lead ECG		X			X		X	Triuplicate measurements.
Vital signs		X			X		X	Refer to Section 8.2.2.
Brief PE		X						
Urine pregnancy test (WCBP only)	X							
Visual check of planned challenge sites	X							Prior to any other study procedures.
Saline and Histamine challenges			X					Histamine to be administered at least 20 cm from any IDM sampling
SP challenge				X				Part 1: Up to 4 SP injections: increasing concentrations of SP at a minimum of 20-min intervals. Part 2: Up to 10 SP injections: 

• up to 4 increasing concentrations of SP at a minimum of 20-min intervals, in duplicate

Visit (V)	V1, V2 (Part 2 only)					Follow-up phone call (5-7 days post last challenge day)	Early withdrawal	Notes
Procedure	Pre-challenge	Within 1 h before first control challenge	At least 20 min before first SP challenge	SP challenges	2 h after last SP challenge			
								
 
• a further 2 SP injections at one concentration may also be given, if ongoing data suggest biopsy samples are required
 

Wheal and flare assessment		See Section 1.3.3						
Blood sample for exploratory biomarkers		X			X			Part 2, V2 only.
IDM		See Section 1.3.3						Part 2 only
Skin punch biopsy		See Section 1.3.3						Part 2, V2 only. May or may not be performed based on ongoing data.
AE review		<===== =====>					X	
SAE review		<===== =====>					X	
Concomitant medication review		X						Review of medications since last visit, if applicable.
Follow-up on possible reactions at sites of IDM/biopsy						X		Part 2 only.

Abbreviations: AE = adverse event; ECG = electrocardiogram; IDM = intradermal microdialysis; SAE = serious adverse event; SP = substance P.

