Histamine intradermal challenge	
Highly sensitised patients may experience stronger local reactions. In extremely rare cases generalised side reactions and even severe systemic reactions (anaphylactic shock) may occur.
 
Mild systemic adverse reactions include rhinitis, conjunctivitis, asthma, generalized exanthema, or urticaria. More severe adverse reactions include itching of tongue, throat, palms or soles. The reaction may progress to cyanosis, tachycardia, dizziness, headache, bronchial constriction, urticaria, asthma, marked hypotension or hypertension, vomiting, urination or defecation.
	
Histamine challenge is an established proinflammation/allergy test.
 
Only small concentrations will be administered via skin prick. One drop (~50 µL) of 1.7 mg/mL solution is applied to the skin and a prick needle is passed through to introduce a small amount intradermally. This dose and technique are commonly used in histamine skin challenge test. The participants will be closely monitored during administration of histamine challenge. The clinical site will have appropriate precautions and treatments in place, per the product label, during administration and post-administration observation.

Potential Risk of Clinical Significance	Summary of Data/Rationale for Risk	Mitigation Strategy
Study Procedures		
Intradermal Microdialysis	Mild pain, bruising and irritation at dialysis site	Site staff under supervision of experienced staff will follow local standard approaches to perform the procedure.
Phlebotomy	Fainting, mild pain, bruising, irritation or redness at a phlebotomy site may be associated with blood draws.	Experienced site staff will follow local standard approaches for managing events related to blood draws.  Participants are instructed to visually inspect phlebotomy sites after clinical visit are informed what signs of inflammation/infection to watch for and contact the investigator with any concerns.

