Skin Biopsy	
Complications of punch skin biopsy are uncommon but may include bleeding, infection, and scarring.
 
Scarring risk is increased in individuals with a history of scarring and in individuals with darker skin.
	
Exclusion criterion #3: History of risk for or actual experience of complications from skin biopsy including excess bleeding, infection, or scarring/keloid formation (Participants with darker skin (Fitzpatrick>2) will be excluded).
 
Observation of the subject while in the clinical unit and at follow-up after discharge from the unit.

Potential Risk of Clinical Significance	Summary of Data/Rationale for Risk	Mitigation Strategy
		Participants are instructed to visually inspect skin biopsy sites after clinical visit and are informed what signs of inflammation/infection to watch for and contact the investigator with any concerns.

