### 2.3.2. Benefit Assessment

There will be no benefit to the participant taking part in this study. However, participants will be contributing to the process of developing new methodologies to assess future medicines by taking part in the study.

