**In Part 2 only:**

- Participants will receive up to 6 additional SP intradermal injections for biomarker analysis:
  - IDM challenges: 4 increasing concentrations of SP (the same concentrations as those administered in the wheal and flare challenges); IDM samples will be taken at the site of each challenge, before and after challenge.
  - Biopsy challenges at Challenge Visit 2: 2 at the same concentration of SP; 3 biopsies would be taken – one from each challenged site and one from a non-challenge area of skin. (these challenges and biopsies may or may not be performed, based on review of ongoing data.)
- Biomarker blood samples will be taken before the first SP challenge and after the last SP challenge at Challenge Visit 2.

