#### **Medical Conditions**

1. Significant history of or current, cardiovascular (including hypotension, severe hypertension, vasomotor instability), respiratory (including asthma), renal, gastrointestinal, endocrine, haematological, infectious or neurological disorders constituting a risk when taking part in the study or interfering with the interpretation of data.

2. History or presence of significant skin disorder (such as but not limited to chronic urticaria, atopic dermatitis, severe eczema, psoriasis or skin cancer).
3. History of risk for or actual experience of complications from skin biopsy including excess bleeding, infection, or scarring/keloid formation.
4. Abnormal blood pressure as determined by the investigator.
5. Alanine transaminase (ALT)  $>1.5 \times$  upper limit of normal (ULN).
6. Total bilirubin  $>1.5 \times$ ULN (isolated bilirubin  $>1.5 \times$ ULN is acceptable if total bilirubin is fractionated and direct bilirubin  $<35\%$ ).
7. Current or chronic history of liver disease, or known hepatic or biliary abnormalities (with the exception of Gilbert's syndrome or asymptomatic gallstones).
8. QT interval corrected for heart rate according to Fridericia's formula (QTcF)  $>450$  msec, based on the mean of triplicate ECGs .

NOTE: The QTc is the QT interval corrected for heart rate according to Fridericia's formula (QTcF).

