## **7. DISCONTINUATION OF STUDY INTERVENTION AND PARTICIPANT DISCONTINUATION/WITHDRAWAL**

### **7.1. Study Stopping criteria**

- If a SAE, considered reasonably attributable to study intervention (SP, histamine) in the opinion of the Investigator, occurs in one participant, then dosing will be temporarily halted, and no further participants will be enrolled or dosed until a full safety review of the data has taken place. Relevant reporting and discussion with the Medical Monitor, relevant site personnel, and the IRB/IEC will take place before resumption of enrolment or dosing.

- If the significant clinical or laboratory abnormality, considered reasonably attributable to study intervention (SP, histamine) in the opinion of the Investigator, occurs in more than 2 participants, then dosing will be temporarily halted, and no further participants will be enrolled or dosed until a full safety review of the data has taken place. Relevant reporting and discussion with the Medical Monitor, relevant site personnel, and the IRB/IEC will take place before resumption of enrolment or dosing.

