## **8. STUDY ASSESSMENTS AND PROCEDURES**

- Study procedures and their timing are summarized in the SoA.
- Protocol waivers or exemptions are not allowed
- Immediate safety concerns should be discussed with the sponsor immediately upon occurrence or awareness to determine if the participant should continue or discontinue study intervention.
- Adherence to the study design requirements, including those specified in the SoA, is essential and required for study conduct.
- All screening evaluations must be completed and reviewed to confirm that potential participants meet all eligibility criteria. The investigator will maintain a screening log to record details of all participants screened and to confirm eligibility or record reasons for screening failure, as applicable.
- Procedures conducted as part of the participant's routine clinical management (e.g., blood count) and obtained before signing of ICF may be utilized for screening or baseline purposes provided the procedure met the protocol-specified criteria and was performed within the time frame defined in the SoA.
- The maximum amount of blood collected from each participant over the duration of the study, including any extra assessments that may be required, will not exceed 500 mL.
- Repeat or unscheduled samples may be taken for safety reasons or for technical issues with the samples.

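### Read literally, the one-SAE halt in Protocol 7.1 covers only SP and histamine, so an SAE attributed solely to a study procedure or to saline forces no study-level pause

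*Protocol*

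**What the plan says.** Protocol 7.1 has two stopping rules. Under the first, dosing and enrolment stop, pending a full safety review, when an SAE "considered reasonably attributable to study intervention (SP, histamine) in the opinion of the Investigator, occurs in one participant". The second applies to a significant clinical or laboratory abnormality in more than 2 participants and uses the same SP-and-histamine parenthesis.

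The risk table in Protocol 2.3.1 deals with SP and histamine as challenge agents and puts IDM, phlebotomy and skin biopsy in a separate block for study procedures. For IDM it lists "Mild pain, bruising and irritation at dialysis site". For biopsy it says "Complications of punch skin biopsy are uncommon but may include bleeding, infection, and scarring". For phlebotomy it lists fainting and mild local effects. Saline has no entry.

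IDM is done at both Part 2 visits. Biopsies are confined to Part 2 Visit 2, and Protocol 4.1 says that "these challenges and biopsies may or may not be performed, based on review of ongoing data". Phlebotomy and saline occur in both parts. On benefit, Protocol 2.3.2 states: "There will be no benefit to the participant taking part in this study".

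**The concern.** The rule turns on what the investigator names as the cause. A serious event attributed to SP stops the study at once until a full safety review is done. The same event attributed only to a biopsy or a microdialysis probe does not, and whether anyone pauses is then left to judgement or to the next scheduled review. The participants are healthy volunteers who gain nothing from taking part, so an automatic pause for a procedure-related SAE would be proportionate.

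Other parts of the protocol use a wider idea of relatedness. Section 8.3 has investigators follow up events related to the study as well as to the intervention. Section 8.3.1 covers late SAEs related to study participation, and 10.3.4 asks for each SAE's relationship to study participation. Only the stopping rule is narrower.

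**Working it through.** The plan states no figure to reproduce, and the sample size is not statistically derived (Protocol 9.2). The check is a reading of the text plus one count.

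**Step 1. Apply 7.1 under one consistent reading at a time.** The parenthesis is either a closed list or an illustration to be filled in from sections 6 and 6.1. Section 6 defines study intervention broadly and mentions medical devices. Section 6.1 lists saline, SP and histamine. Section 6.2 mentions a biomarker sampling device among its handling items.

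| SAE attributed solely to | Closed list | Illustrative list |
|---|---|---|
| SP or histamine | halt | halt |
| Saline injection | no mandatory halt | halt, via 6 and 6.1 |
| IDM | no mandatory halt | arguable at best: a device, but not listed in 6.1 |
| Skin biopsy | no mandatory halt | no mandatory halt |
| Phlebotomy | no mandatory halt | no mandatory halt |

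The gap for biopsy and phlebotomy holds under both readings. The gap for saline and IDM depends on the literal one.

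**Step 2. Look for another mandatory, event-driven, study-level pause.**

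- Exclusion criterion 3 removes people with "History of risk for or actual experience of complications from skin biopsy including excess bleeding, infection, or scarring/keloid formation". This is preventive.
- Section 8 sends immediate concerns to the sponsor "to determine if the participant should continue or discontinue study intervention". This concerns one participant.
- Section 8.3.1 requires SAE reports within 24 hours, and 10.1.1 requires IRB/IEC notification under that body's procedures. These inform but do not halt.
- Section 1.3.3 allows the timing and number of Part 2 assessments, including IDM and biopsy samples, to be altered on new data. Section 4.1 lets the biopsies be omitted. These act at study level but are optional.
- Section 10.1.9 lets the sponsor terminate and the investigator initiate site closure. Both are discretionary.
- The Part 2 phone call 5 to 7 days after the last challenge covers "Follow-up on possible reactions at sites of IDM/biopsy". It detects events and triggers no halt.
- SAP 4.7, Table 1, lets data review 2 stop or pause the study on safety data. It is tied to about 10 completers, and Protocol 9.5 lets enrolment continue during it.

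None is mandatory, event-driven and study-level at once.

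**Step 3. Worst-case count for Part 2.** Inputs: review 2 at about 10 Part 2 completers (Protocol 9.5; SAP Table 1); the first Part 2 participant has the SAE; nobody uses any of the discretion in Step 2.

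- If that participant still completes both visits: 10 − 1 = about 9 others complete before review 2.
- If that participant is withdrawn and is not a completer: 10 − 0 = about 10 others. This mainly fits an IDM event at Visit 1.

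The count covers completers only; others might already have had IDM at Visit 1. For biopsy it also assumes that biopsies are done at all. In Part 1, where phlebotomy and saline are the relevant items, reviews fall at about 3, 6 and 12 completers, so the longest interval between them is 12 − 6 = 6 completers.

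**The case against.** The strongest reply is that a rule which halts dosing may sensibly be tied to the agents dosed. Procedures with mild or uncommon complications can be left to medical judgement, especially when SAEs reach the sponsor within 24 hours and Part 2 sampling can be altered or dropped on new data. That stands as a reason to rate the point low. It does not make a pause mandatory.

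A second reply is that attribution solely to a procedure is narrow. IDM is done at SP or saline sites, and two of the three biopsies are at SP-injected sites, so SP may often be named as well, and then the halt applies. This also stands, with two limits. The third biopsy is from unchallenged skin. And 10.3.3 asks for positive grounds for a causal link, not merely that one cannot be excluded, so sharing a site with SP does not settle attribution.

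A third reply is that a wider trigger has limited reach for biopsy. Scheduled SAE collection ends 2 h after the last SP challenge, and infection or scarring would usually appear later. This stands, and it is why the fix addresses events learned of later.

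A reader might infer that the plan leaves procedure-related SAEs without any response, or that 7.1 contradicts the definition in section 6. The documents support neither. Several safeguards exist, as listed in Step 2, and a stopping rule may be narrower than a general definition without conflicting with it.

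**Conclusion.** The point holds as a limit on one rule. Read literally, 7.1 requires no study-level pause after an SAE attributed solely to IDM, skin biopsy, phlebotomy or saline. Biopsy and phlebotomy are outside the rule on either reading; saline is arguably inside it through sections 6 and 6.1.

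The size is small. No complication rate is given, so the probability of such an SAE cannot be estimated. It is probably low, since IDM effects are described as mild, biopsy complications as uncommon, and the biopsies are optional and at most 3 mm across (Protocol 8.7). Up to 20 Part 2 completers, plus any replacements, could have IDM or biopsy. Phlebotomy and saline reach both parts, up to 12 + 20 = 32 participants before replacements.

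The figure of about 9 to 10 others should not be read as an expected number. It rests on the first Part 2 participant being affected and on nobody acting despite prompt reporting. No endpoint or analysis is affected. This is an inexpensive improvement that the sponsor could make, not an error it must correct.

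**What to change.** Amend the first bullet of 7.1 only:

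- Extend the parenthesis to SP, histamine and saline, and add as an alternative cause a study procedure (IDM, skin biopsy, phlebotomy). Adding saline removes the doubt about how the parenthesis should be read.
- State that the safety review may suspend only the implicated procedure, for example by dropping the optional biopsies while SP challenges resume.
- State that an SAE the investigator learns of after the 2 h collection window, for example at the 5-7 day call, counts toward the trigger. The window in 8.3.1 need not change.

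Leave the second bullet as it is. Bruising and irritation are expected with IDM and bleeding is a listed biopsy risk, so widening a rule based on abnormalities in more than 2 participants could halt the study for expected local effects.

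The cost is a protocol amendment with IEC/IRB approval (10.1.1), an instruction to the site to record procedure attribution for SAEs, and possibly a temporary pause. The instruction is needed because 10.3.3 frames causality against study intervention, although 10.3.4 already asks about study participation. The relatedness tables in SAP 4.5.2, split by SP and histamine, need no change for the trigger to work.

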## **7.2. Discontinuation of Study Intervention**

In rare instances, it may be necessary for a participant to permanently discontinue study intervention. If study intervention is permanently discontinued, the participant will remain in the study until the end of that challenge visit to be evaluated for safety. See the SoA for data to be collected at the time of discontinuation of study intervention and follow-up and for any further evaluations that need to be completed.

## **7.3. Participant Discontinuation/Withdrawal from the Study**

- A participant may withdraw from the study at any time at his/her own request or may be withdrawn at any time at the discretion of the investigator for safety, behavioural, compliance or administrative reasons. This is expected to be uncommon.
- At the time of study discontinuation, the participant should undergo the assessments for early withdrawal shown in the SoA.
- The participant will be permanently discontinued both from the study intervention and from the study at that time.
- If the participant withdraws consent for disclosure of future information, the sponsor may retain and continue to use any data collected before such a withdrawal of consent.
- If a participant withdraws from the study, he/she may request destruction of any samples taken and not tested, and the investigator must document this in the site study records.

## **7.4. Lost to Follow Up**

A participant will be considered lost to follow-up if he or she repeatedly fails to return for scheduled visits and is unable to be contacted by the study site.

The following actions must be taken if a participant fails to return to the clinic for a required study visit:

- The site must attempt to contact the participant and reschedule the missed visit as soon as possible and counsel the participant on the importance of maintaining the assigned visit schedule and ascertain whether or not the participant wishes to and/or should continue in the study.

- Before a participant is deemed lost to follow up, the investigator or designee must make every effort to regain contact with the participant (where possible, 3 telephone calls and, if necessary, a certified letter to the participant's last known mailing address or local equivalent methods). These contact attempts should be documented in the participant's medical record.
- Should the participant continue to be unreachable, he/she will be considered to have withdrawn from the study with a primary reason of lost to follow-up.

## **8. STUDY ASSESSMENTS AND PROCEDURES**

- Study procedures and their timing are summarized in the SoA.
- Protocol waivers or exemptions are not allowed
- Immediate safety concerns should be discussed with the sponsor immediately upon occurrence or awareness to determine if the participant should continue or discontinue study intervention.
- Adherence to the study design requirements, including those specified in the SoA, is essential and required for study conduct.
- All screening evaluations must be completed and reviewed to confirm that potential participants meet all eligibility criteria. The investigator will maintain a screening log to record details of all participants screened and to confirm eligibility or record reasons for screening failure, as applicable.
- Procedures conducted as part of the participant's routine clinical management (e.g., blood count) and obtained before signing of ICF may be utilized for screening or baseline purposes provided the procedure met the protocol-specified criteria and was performed within the time frame defined in the SoA.
- The maximum amount of blood collected from each participant over the duration of the study, including any extra assessments that may be required, will not exceed 500 mL.
- Repeat or unscheduled samples may be taken for safety reasons or for technical issues with the samples.

### **8.1. Efficacy Assessments**

Not applicable.

### **8.2. Safety Assessments**

Planned time points for all safety assessments are provided in the SoA.

#### **8.2.1. Physical Examinations**

- A complete physical examination will include, at a minimum, assessments of the Skin, Cardiovascular, Respiratory, Gastrointestinal and Neurological systems. Height and weight will also be measured and recorded.

- A brief physical examination will include, at a minimum, assessments of the skin, lungs, cardiovascular system, and abdomen (liver and spleen).

### **8.2.2. Vital Signs**

- Tympanic body temperature, pulse rate and blood pressure will be assessed as a single or triplicate measurement(s), as described below.
- Blood pressure and pulse measurements will be assessed in a semi-supine position with a completely automated device. Manual techniques will be used only if an automated device is not available.
- Blood pressure and pulse measurements should be preceded by at least 5 minutes of rest for the participant in a quiet setting without distractions (e.g., television, cell phones).
- At screening, vital signs will consist of 1 temperature, and 3 pulse and blood pressure measurements. On Challenge days, vital signs will consist of 1 pulse and 3 blood pressure measurements. Vital signs will be taken before blood collection for laboratory tests. Triplicate readings will consist of 3 consecutive pulse and/or blood pressure readings recorded at intervals of at least 1 minute.

